units of intradetrusor botulinum toxin A. A primary endpoint of 12 weeks showed a significant decrease in daily episodes of UUI episodes in the botulinum toxin A group compared to placebo [6,7]. Another double-blind, double-placebo-controlled, randomized trial compared anticholinergic use versus botulinum toxin A which showed a decrease in the number of episodes of UUI in the active group without any significant difference between treatments [8]. In this trial, both groups showed no significant differences in improvement in quality of life, but only 13% of patients in the anticholinergic group and 27% in the botulinum toxin A group reported complete resolution of UUI episodes [8]. Thus, we believe there is much room for improvement in the treatment of OAB symptoms.

Hydrodistention has been a treatment modality for interstitial cystitis (IC) since the early 1900s [9, 10]. It is thought that any efficacy for the treatment of IC is probably related to damage to mucosal afferent nerve endings in the bladder [11]. There are very limited studies on the use of hydrodistention for urgency and OAB symptoms. Dunn et al in a small study found that 14 of 20 patients with urgency and UUI reported resolution of their symptoms after prolonged bladder distention [12]. They also found that the bladder capacity in all patients increased after hydrodistention. In a retrospective review of patients undergoing hydrodistention, Cole et al found that in patients who had undergone the procedure for frequency and urgency symptoms with no pain component, 50% at 1 month, 19% at 3 months, and 7% at 6 months reported improvement in symptoms [13]. Other studies have shown no benefit from hydrodistention in the treatment of urgency and OAB symptoms [14, 15].

There are currently no studies investigating hydrodistention at the time of intradetrusor botulinum toxin A in patients with refractory OAB symptoms. We believe that patients may have additive benefit from a hydrodistention performed with botulinum toxin A injection as the

increased bladder capacity gained by the distention will be sustained for a longer period of time in the setting of botulinum toxin A.

Significance

No studies have been performed examining hydrodistention in the setting of intradetrusor botulinum toxin A for the treatment of refractory OAB symptoms.

Study Design

Inclusion criteria

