1. Women with refractory overactive bladder symptoms, failing a credible behavioral therapy intervention and medical therapy or not tolerating medical therapy. Patients who are on medical therapy will stop the medical therapy for at least 2 weeks prior to botulinum toxin A treatment in the study
2. Female \geq 18 years old
3. Desires further treatment for OAB symptoms.
4. Express understanding and ability to perform clean intermittent self-catheterization (CISC) if required.
5. Ability to consent
6. Ability to complete all study related items and interviews

Exclusion Criteria

1. Post void residual urine volume > 150 mL as assessed by catheter or ultrasound
2. History of intradetrusor botulinum toxin A injection
3. History of or current cancer of the genitourinary or gynecology tract

4. Neurogenic bladder
5. Interstitial cystitis
6. Current urinary tract infection (can be treated and re-considered for study)
7. Current active sacral neuromodulation device
8. Non-English speaking
9. History of chronic pelvic pain
10. Hematuria not previously evaluated

Intervention

Hydrodistention at a pressure of 80 cm H₂O for 5 minutes prior to intradetrusor injection of 100 units of botulinum toxin A (hydrodistention group) or intradetrusor injection of 100 units of botulinum toxin A alone (botulinum toxin A alone group).

Primary outcome

The primary outcome will be measured as change from baseline at 12 weeks using the OAB-q bother subscale which consists of eight questions assessing symptom bother with a possible score from 0 to 100 with a higher score indicating greater symptom bother.

Secondary outcomes

1. Number of UUI episodes as reported in a 3-day bladder diary at 12 weeks as measured in change from baseline.
2. Total number of voids reported in the 3-day bladder diary at 12 weeks as measured in change from baseline.

3. Proportion of subjects requiring clean intermittent self-catheterization (CISC) post-operatively as reported at 2 week post-operative visit. CISC will be initiated at post-void residual volumes of > 300 mL *or* > 150 mL in the presence of bothersome retention symptoms.
4. Post-void residual volume (PVR) at the 2 week follow-up visit measured with catheter or bladder scan.

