5. Rate of urinary tract infection (UTI) as assessed by positive urine culture in patients having symptoms (dysuria, urgency, frequency, temperature ≥ 38 degrees Celcius, and/or suprapubic pain) at the 2 weeks post-operative visit. Subjects who call throughout the study complaining of symptoms but are unable to give a urine culture in clinic will also be treated and reported as having had a UTI.
6. Health related quality of life (HRQL) will be measured as a change from baseline at 12 weeks using the OAB-q HRQL subscale part which consists of 25 questions that assess HRQL addressing coping, concern, sleep, and social interaction where the scoring scale is from 0 to 100 with a higher score indicating a better quality of life.
7. Patient global impression of improvement at 12 weeks as measured using the Patient Global Impression of Improvement Questionnaire (PGI-I).
8. Patient satisfaction at 12 weeks as measured using Patient Satisfaction Questionnaire (PSQ).
9. Subjective outcome at 24 weeks using the OAB-q

Protocol in detail

Women seen in the urogynecology and urology clinics at University of Alabama at Birmingham who are seeking treatment for refractory OAB symptoms will be screened. Patients

who have failed a credible behavioral therapy intervention and medical therapy or not tolerating medical therapy will be evaluated for this study. Those patients satisfying the inclusion/exclusion criteria will be offered to participate in the study. Informed consent will be reviewed and signed with patients wishing to proceed.

At enrollment, any subjects who are using medical therapy including anticholinergic or β_3 agonist medications will stop these therapies for at least 2 weeks prior to treatment. Baseline clinical data including OAB-q and a 3 day bladder diary will be collected as well as clinical and demographic information. Data from subjects' urodynamic testing will be abstracted from the clinical chart if performed within the prior 12 months of the enrollment date. If no urodynamics testing is available then we will not collect this information for those subjects. Subjects will also be counseled on the possible need for clean intermittent self-catheterization (CISC) and instructions on how and when to perform CISC will be given in clinic. Subjects will be randomized the day of the scheduled procedure. Subjects will be blinded to which group they are assigned.

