Subjects randomized to the botulinum toxin A alone group will undergo intradetrusor injection of 100 units of botulinum toxin A diluted in 10 cc of sterile normal saline and injected in volumes of 0.5cc in a grid-like pattern using rigid cystoscopy in the operating room under monitored anesthesia care (MAC) or general anesthesia. Those subjects randomized to the hydrodistention group will undergo hydrodistention of the bladder in the operating room just prior to the botulinum toxin A injection. The hydrodistention will be performed with a water pressure of 80 cm H₂O as measured by the height of the sterile water source above the pubic symphysis in the operative room. The bladder will be filled and noted to be full as evidenced by no further influx of water into the bladder. The bladder will be emptied and this volume will be

recorded as initial bladder volume. The hydrodistention will then be performed with the bladder filled at a pressure of 80 cm H₂O and noted to be full as evidenced by no further influx of water into the bladder. This volume will be held in the bladder for 5 minutes. Upon emptying, the volume will be recorded as the hydrodistention volume. After the hydrodistention, these subjects will then receive intradetrusor injection of 100 units of botulinum toxin A in a grid like pattern using rigid cystoscopy as described above.

Subjects will be seen for a 2 week post-operative visit. It will be recorded if subjects have had to use CISC including how many days. CISC will be initiated at post-void residual volumes of > 300 mL *or* > 150 mL in the presence of bothersome retention symptoms. Subjects with symptoms of UTI including dysuria, urgency, frequency, temperature \geq 38 degrees Celsius and/or suprapubic pain will have urine culture sent and treated accordingly for UTI. If subjects call with symptoms of urinary tract infection but are unable to present for urine culture will also be treated and reported as an UTI.

Subjects will follow up for scheduled post-operative care at a 6 and 12 weeks at which time they will complete the OAB-q, PGI-I, and PSQ for the 12 week primary outcome data. Subjects will complete a 3 day bladder diary during the week prior to the 12 week visit and bring the information with them to the visit. At the 24 week follow up visit, patients will complete the OAB-q. All follow up visits at 2 weeks, 6 weeks, 12 weeks, and 24 weeks will be plus or minus a 1 week window from the date of procedure.

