Randomization/Allocation

Patients will be randomized to the hydrodistention group or botulinum toxin A alone group in a 1:1 fashion using variable size permuted blocks of 4, 6, and 8. This will be done by a

member of the research team on the day of the procedure. Subjects will be blinded to which group they are assigned. Allocation concealment will be ensured by using a centralized service to provide sequentially numbered, opaque, sealed envelopes.

Confidentiality

Extensive efforts will be made to ensure and maintain participant confidentiality. All identifying information will be maintained in a secure area at all times. Participants will be assigned a Study ID number at study enrollment taken from the randomization log. This Study ID will be used to label all data collection sheets.

Power analysis

A sample size of 27 patients per group provides 80% power to detect a difference of 15 points or more at a 0.05 level of significance. For this determination, we estimated the mean OAB-q bother score in the control group to be 45 and the standard deviation of the change in severity scores to be 19 points based on a prior studies by Coyne, et al [16, 17]. We hypothesized a 15 point difference to be meaningful based on feasibility, clinical significance, and prior reported minimally important difference (MID) [17]. Allowing for a 10% dropout rate, we will recruit a total of 60 patients, 30 per group.

Data analysis

Demographics and baseline data will be analyzed by Student's paired t-test and chi-squared test or Fisher's Exact test as appropriate.

Project schedule

- February to May 2016: start up and obtain IRB approval

- May 2016 until August 2017: Recruitment and Enrollment
- September 2017 to March 2018: Data analysis, manuscript completion

References for OAB Hydro

2. Haylen BT, de Ridder D, Freeman RM, et al. An International Urogynecological Association (IUGA)/International Continence Society (ICS) joint report on the terminology for female pelvic floor dysfunction. *Int Urogynecol J*. 2010;21:5.

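### Do the 6-week questionnaires need a stated purpose and a pre-specified 6-week comparison?

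*Combined protocol and SAP*

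**What the plan says.** Under Protocol in detail, subjects are seen at 2, 6, 12 and 24 weeks, each with a one-week window either side. The questionnaire sentence covers two of those visits together: "6 and 12 weeks at which time they will complete the OAB-q, PGI-I, and PSQ for the 12 week primary outcome data". The next sentence ties the bladder diary to the 12-week visit alone, and the 24-week visit carries the OAB-q only.

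The outcome lists are specific about timing. For the primary outcome: "The primary outcome will be measured as change from baseline at 12 weeks using the OAB-q bother subscale". OAB-q quality of life (secondary outcome 6) is also a 12-week change. Items 7 and 8 are "Patient global impression of improvement at 12 weeks" and "Patient satisfaction at 12 weeks". Item 9 is "Subjective outcome at 24 weeks using the OAB-q". The remaining secondary outcomes come from the 12-week diary or centre on the 2-week visit. None is set at 6 weeks.

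The Data analysis section is a single sentence beginning "Demographics and baseline data will be analyzed by". It gives no method for any follow-up outcome, at 6 weeks or any other time.

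**The concern.** On a literal reading, subjects complete the OAB-q, PGI-I and PSQ at week 6 and the plan never says why. Two things could follow.

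First, an unplanned time point invites selective reporting: a favourable 6-week difference could be brought forward and an unfavourable one left out.

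Second, the Background rationale is about duration, namely that the "increased bladder capacity gained by the distention will be sustained for a longer period of time in the setting of botulinum toxin A". The one time course cited there, a retrospective review of hydrodistention without botulinum toxin A, has 50% of patients improved at 1 month and 19% at 3 months. If any added benefit follows a similar course, a null at 12 weeks might hide an early effect that had worn off, and a planned 6-week contrast might seem the natural way to tell. Week-6 scores could also support the estimate for subjects who miss week 12.

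**Working it through.** **What the sentence supports.** Two readings are possible.

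- *Forms at both visits.* Both visits are named before the forms are listed, week 6 has its own window, and the diary sentence shows that the authors could limit an instrument to week 12 when they wished.
- *Forms at week 12 only.* The purpose clause names only the 12-week data, and the outcome lists agree with it.

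The text does not settle the matter. On the second reading nothing is collected and left unused. On the first, the extra responses sit beside the 12-week comparison and do not alter it.

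**Inputs.** From Power analysis: 27 evaluable per group, a 15-point difference, SD of change 19, significance level 0.05 (taken as two-sided), 10% dropout, 30 recruited per group. Assumptions, because the documents give neither: an SD of 19 at week 6 as well, and a correlation ρ of 0.5 to 0.7 between the 6- and 12-week changes.

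**The plan's own figure.** A two-sample t-test with standardised difference 15/19 = 0.789 needs 26.2 per group, so 27, with 81.2% power. Then 27/0.90 = 30 per group, 60 in all. The stated sample size reproduces, and it depends on week 12 alone.

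**Precision of a 6-week contrast.**

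- SE = 19 × √(2/27) = 5.17.
- t(0.975, 52 df) = 2.007, so the 95% CI half-width is 2.007 × 5.17 = 10.4 points.
- If the true 6-week difference were zero, the interval would exclude 15 points about 81% of the time, by symmetry with the power above.
- If the true difference were 10 points, power would be about 48%.

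Such a contrast could rule out about 15 points. It could not reliably tell a smaller early effect from none.

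**Fading between 6 and 12 weeks.** The SD of the within-subject change from week 6 to week 12 is 19 × √(2(1 − ρ)). At 27 per group, 80% power needs a standardised difference of 0.777.

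| ρ | SD | Change in group difference detectable with 80% power |
|---|---|---|
| 0.5 | 19.0 | 14.8 points |
| 0.6 | 17.0 | 13.2 points |
| 0.7 | 14.7 | 11.4 points |

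Fading would have to approach the whole 15-point target effect before the trial could detect it with 80% power.

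**Support for missing week-12 data.** Take the best case, in which all 3 per group who miss week 12 (10% of 30) have week-6 scores. The effective number per group is 27/(1 − ρ² × 3/30).

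| ρ | Effective n per group | Power for 15 points |
|---|---|---|
| none used | 27 | 81.2% |
| 0.5 | 27.7 | 82.2% |
| 0.6 | 28.0 | 82.7% |
| 0.7 | 28.4 | 83.2% |

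The gain is 1 to 2 percentage points.

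**Cost of a formal addition.** A 6-week contrast on OAB-q bother, PGI-I and PSQ is at least three further comparisons in a trial of 60 subjects.

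**The case for a change.** The best case for a change is that either reading calls for an edit. If week 6 is intended, the data have no declared use. If it is not, the sentence is wrong. The edit costs almost nothing, 12 weeks would stay the sole primary time point, and declaring the 6-week results in advance would remove the chance to pick them afterwards. The duration rationale gives week 6 some scientific interest.

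Parts of this stand. The sentence is ambiguous, no outcome or analysis refers to week 6, and the missing-data model would displace no stated method.

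The rest is weaker. Nothing in the protocol signals an intention to report week 6, so the selective-reporting risk is hypothetical. The outcome lists would also expose it, because any 6-week comparison would plainly fall outside them. Durability already has a later outcome, the 24-week OAB-q. The cited time course has no botulinum toxin A and no between-group effect, and the same section cites studies that found no benefit from hydrodistention. Choosing a repeated-measures model for the primary contrast is a larger decision than a note on the 6-week visit can carry. It belongs with the separate question of how the 12-week outcome will be analysed, which the plan leaves open.

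**Conclusion.** No change to the plan follows. The observation is accurate as far as it goes: the follow-up sentence is loosely worded, and week 6 appears in no outcome. But the primary time point is stated clearly, the sample size of 27 evaluable and 30 recruited per group rests on it, and neither depends on whether the forms are completed at week 6. If 6-week responses exist, treating them as exploratory is the ordinary course, and the outcome lists already imply it.

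A formal 6-week contrast would give limited information: a CI of about ±10.4 points, about 48% power for 10 points, and no dependable evidence of fading below a change of about 11 to 15 points. The missing-data gain is at most about 2 percentage points of power. These figures assume the protocol's SD of 19 also holds at week 6 and a within-subject correlation of 0.5 to 0.7. The conclusion would not survive if the report put forward a 6-week result as confirmatory, but nothing in the documents suggests that.
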